## **8. ENDPOINTS AND STATISTICAL ANALYSIS**

### **8.1. General Statistical Considerations**

Unless otherwise specified, all analyses will be performed on the ITT population defined as all subjects who are randomized and received at least 1 dose of study agent. The ITT analysis will be performed according to the treatment that a subject was randomized to receive, regardless of the actual treatment received.

The database will be locked for primary analysis after the data through the Day 364 (Week 52) visit for all subjects have been collected, verified, and validated. All subjects and study site personnel will remain blinded until the final database lock and the primary efficacy results become public.

All statistical tests will be 2-sided and performed at an overall significance level of 0.05.

### **8.2. Randomization Procedure and Assignment to Treatment Groups**

This is a Phase 3/4, multi-center, randomized, double-blind, placebo-controlled study. Once subjects have consented, have undergone all screening procedures, and have been determined to be eligible for the study, they will return for the Day 0 visit to be randomly assigned (via an interactive voice or web response system [IVRS/IWRS]) to 1 of 2 treatment groups (belimumab or placebo control) in a 2:1 ratio. The randomization will be stratified by screening SELENA SLEDAI score (8-9 vs  $\geq 10$ ), complement level (C3 and/or C4 low vs other), and region (US/Canada vs rest of the world).

### **8.3. Independent Data Monitoring Committee (IDMC)**

An Independent Data Monitoring Committee (IDMC) will review unblinded safety data for this Phase 3/4 study on an ongoing basis until the data are locked and analyzed through Week 52. The IDMC will include at least 3 physicians, and a statistician, none of whom are affiliated with the sponsor. Events to be monitored during the safety review include, at a minimum, all serious adverse events (including deaths, serious psychiatric events, and serious infections), Grade 3 and Grade 4 laboratory abnormalities, opportunistic infections (serious and nonserious), malignancies, and hypersensitivity/anaphylactic reactions. The 1st IDMC data review meeting will occur after the first 100 subjects have been treated through Day 56, or within 6 months of the treatment of the 1st subject, whichever is earlier. After the initial review, the committee will review the data approximately every 6 months. At all times the sites and sponsor will remain blinded to treatment allocation. Investigators and IRBs/IECs, as appropriate, will be notified of the outcome of each IDMC meeting.

The IDMC will receive information within 72 hours of the sponsor or designee receiving notification of all SAEs that are life threatening or result in death. Other SAEs will be provided monthly to the IDMC.

After Week 52, the monitoring may be assumed by an internal GSK/HGS committee.

## 8.4. Sample Size Rationale

Approximately 501 subjects will be randomized and treated in the study, with a target of at least 334 subjects in the arm receiving belimumab and 167 subjects in the arm receiving placebo. This sample size provides at least 90% power at a 5% level of significance to detect a minimum of a 15.55% absolute improvement in the SRI response rate with the modified SLEDAI-2K scoring for proteinuria for the 10 mg/kg belimumab group relative to the placebo group (assumed rate =43.95%) at Week 52. This sample size is also sufficient to provide approximately 80% power at a 5% level of significance to detect a minimum of a 13.4% absolute improvement in the SRI response rate with the SELENA SLEDAI scoring for proteinuria for the 10 mg/kg belimumab group relative to the placebo group (assumed rate = 44.8%).

The selection of the assumed treatment differences is based on the observed SRI data from studies BEL112341 (HGS1006-C1115/BLISS SC) and BEL113750 (Northeast Asia), which are two efficacy studies that concluded in 2015 and 2016, respectively, and have nearly identical eligibility criteria to study HGS1006-C1112 including requiring a screening SS score  $\geq 8$ . SRI results, calculated using the SS results and calculated using a modification to the proteinuria scoring based on SLEDAI-2K rules, are shown in [Table 8-1](#).

**Table 8-1 SRI Results From Studies BEL112341 and BEL113750**

	SRI Calculated Using the SS Results as Collected			SRI Calculated Using SS Results with the Modified SLEDAI-2K Proteinuria Scoring		
Dataset	Placebo	Belimumab	$\Delta$	Placebo	Belimumab	$\Delta$
BEL112341*	48.4%	61.4%	12.98%	46.6%	61.7%	15.14%
BEL113750**	40.1%	54.3%	14.17%	40.2%	56.3%	16.16%
Pooled BEL112341 and BEL113750	44.8% (222/496)	58.2% (582/1000)	13.44%	43.95% (218/496)	59.50% (595/1000)	15.55%

\* Inclusion criterion SS $\geq 8$ , 200 mg SC dose used.

\*\*Inclusion criterion SS $\geq 8$ , 10 mg/kg IV dose used.

All sample size calculations were performed using Power Analysis and Sample Size software (PASS 2012).

## **8.5. Efficacy**

### **8.5.1. Primary Efficacy Endpoint**

The primary efficacy endpoint is the systemic lupus erythematosus responder index (SRI) response rate with the modified SLEDAI-2K scoring for proteinuria at Week 52.

A SRI response is defined as:

- $\geq 4$  point reduction from baseline in SELENA SLEDAI score (with the modified SLEDAI-2K scoring for proteinuria),

**AND**

- No worsening (increase of  $< 0.30$  points from baseline) in Physician's Global Assessment (PGA),

**AND**

- No new BILAG A organ domain score or 2 new BILAG B organ domain scores compared with baseline at the time of assessment (ie, at Week 52).

### **8.5.2. Primary Efficacy Analysis**

The proportion of subjects achieving a treatment response at Week 52 will be compared between the belimumab treatment group and placebo using a logistic regression model. The independent variables in the model will include treatment groups (ie, belimumab vs placebo), baseline SELENA SLEDAI score ( $\leq 9$  vs  $\geq 10$ ), baseline complement level (C3 and/or C4 low vs other), and region (US/Canada vs rest of the world). However, the adjustment will not occur for any of these baseline randomization factors that has  $< 10$  responders or  $< 10$  non-responders in a stratification level ([Peduzzi](#) et al, 1996). The analysis will be performed on the intention-to-treat (ITT) population, defined as all subjects who are randomized and treated with at least 1 dose of study agent. The ITT analysis will be performed according to the treatment that a subject was randomized to receive, regardless of the actual treatment received.

Any subject who withdraws from the study prior to the Day 364 (Week 52) visit, misses the Day 364 (Week 52) visit ( $\pm 28$  day window allowed), and/or starts a prohibited medication or dose (see Section [5.5.2](#)) prior to the Day 364 (Week 52) visit will be considered a nonresponder for the Week 52 primary efficacy analysis.

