## **4. INCLUSION AND EXCLUSION CRITERIA**

### **4.1. Inclusion Criteria**

Subjects enrolled in the study must meet the following inclusion criteria:

1. Are at least 18 years of age.
2. Are self-identified black race.
3. Have a clinical diagnosis of SLE according to the American College of Rheumatology (ACR) criteria (see [Appendix 1](#)).
4. Have active SLE disease defined as a SELENA SLEDAI score  $\geq 8$  at screening (refer to [Appendix 5](#) and Section 6.8.1.1 Scoring for Proteinuria for Eligibility at Screening).
5. Have 2 unequivocally positive autoantibody test results defined as a positive antinuclear antibody (ANA) test [ie, titer  $\geq 1:80$  by HEp-2 immunofluorescence assay (IFA) and/or positive enzyme immunoassay (EIA)] and/or a positive anti-dsDNA ( $\geq 30$  IU/mL) serum antibody test as follows:

- from 2 independent time points within the study screening period. Screening results must be based on the study's central laboratory results.

OR

- One positive historical test result and 1 positive test result during the screening period.  
Historical documentation of a positive ANA test (eg, HEp-2 IFA or EIA) or anti-dsDNA (eg, anti-dsDNA by any validated commercial assay) must include the date and type of the test, the name of the testing laboratory, numerical reference range, and a key that explains values provided as positive vs negative OR negative, equivocal/borderline positive). Only unequivocally positive values as defined in the laboratory's reference range are acceptable; borderline values will not be accepted.

6. Are on a stable SLE treatment regimen consisting of any of the following medications (alone or in combination) for a period of at least 30 days prior to Day 0 (ie, day of 1st dose of study agent) [Refer to Section [5.5.1](#) for allowable medications and maximum dose]:

- Corticosteroids (prednisone or prednisone equivalent, up to 40 mg/day):
  - For subjects on SLE combination therapy, their stable steroid dose must be fixed within the range of 0 to 40 mg/day (prednisone or prednisone equivalent).
  - For subjects whose only SLE treatment is steroids, their stable steroid dose must be fixed within the range of 7.5 to 40 mg/day (prednisone or prednisone equivalent).
  - For those subjects on alternating day doses of steroids, use the average of 2 daily doses to calculate the average daily steroid dose.

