#### **8.5.5. Secondary Efficacy Analyses**

The SRI response rate with the SELENA SLEDAI scoring for proteinuria at Week 52 will be compared between the belimumab treatment group and the placebo group using the same analysis methods as described for the primary endpoint in Section [8.5.2](#).

The time to the 1st severe SLE flare over 52 weeks will be compared between the belimumab treatment group and the placebo group using the Cox proportional hazard model. The independent variables in the model will include treatment groups (ie, belimumab vs placebo), baseline SELENA SLEDAI score ( $\leq 9$  vs  $\geq 10$ ), complement level (C3 and/or C4 low vs other), and region (US/Canada vs rest of the world). However, the adjustment will not occur for any of these baseline randomization factors that has < 10 events (ie, severe flares) or < 10 non-events in a stratification level. If a subject withdraws from the study or completes the study up to the Day 364 (Week 52) visit without any severe SLE flare, time to the 1st severe SLE flare will be censored at the time of the last observation. If a subject receives a dose of protocol prohibited/restricted medication that results in treatment failure designation up to the Week 52 visit, the subject will be considered as having a severe SLE flare at the time the medication is started.

The percent of subjects with average prednisone dose that has been reduced by  $\geq 25\%$  from baseline to  $\leq 7.5$  mg/day during Weeks 40 through 52 will be compared between the belimumab treatment and the placebo groups using a logistic regression model. The independent variables in the model will include treatment groups (ie, belimumab vs placebo), baseline SELENA SLEDAI score ( $\leq 9$  vs  $\geq 10$ ), complement level (C3 and/or C4 low vs other), and region (US/Canada vs rest of the world). However, the adjustment

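### The primary model uses baseline disease activity only through one cut at 9/10; adding the continuous Day 0 score on the endpoint's own scoring could give a small power gain at little cost

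*Protocol*

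**What the plan says.** Protocol section 8.5.2 fixes the covariates of the primary analysis: "The independent variables in the model will include treatment groups (ie, belimumab vs placebo), baseline SELENA SLEDAI score", dichotomised at 9/10, then baseline complement and region. The Synopsis gives the same model. The cut mirrors the one used to stratify randomisation on the screening score (section 8.2) and the planned subgroup cut (section 8.5.2.1).

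The score component of response in section 8.5.1 is a "point reduction from baseline in SELENA SLEDAI score (with the modified SLEDAI-2K scoring for proteinuria") of at least 4 points. Response also needs no PGA worsening and no new BILAG A or two new B scores. Under section 8.5.2, withdrawal, a missed Week 52 visit or prohibited medication counts as non-response.

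Activity at entry is set on the screening visit only. Inclusion criterion 4 in section 4.1 reads "Have active SLE disease defined as a SELENA SLEDAI score" of at least 8 at screening. Major secondary endpoint 1, SRI with SELENA proteinuria scoring, is compared "using the same analysis methods as described for the primary endpoint" (section 8.5.5), so it inherits the same covariates.

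**The concern.** One component of the endpoint is defined as a fall from a baseline number, yet the model sees that number only as low or high. A Day 0 score of 10 and one of 20 are treated alike, as are 9 and 3. A total that cannot go below zero cannot fall by 4 from a start below 4.

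Scores under 8 at Day 0 are foreseeable. Entry depends on screening, which may be up to 35 days earlier (section 6.1). The lower model level is at most 9, whereas the lower randomisation stratum is 8-9. Section 6.8.1.2.1 shows one route: proteinuria that improves by the next visit goes from 4 points to 0.

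The covariate as written is also the SELENA-scored total, while the outcome is measured from the total with modified SLEDAI-2K proteinuria scoring. Section 8.5.2 does not say that the covariate follows the endpoint.

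At stake is a modest amount of power that data already collected could supply.

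**Working it through.** **The plan's own figure.** Inputs from sections 8.1 and 8.4 and Table 8-1: "All statistical tests will be 2-sided and performed at an overall significance level of 0.05"; the power claim, "This sample size provides at least 90% power at a 5% level of significance"; a target difference of 15.55 percentage points; placebo rate 43.95%; belimumab 43.95% + 15.55% = 59.50%; 334 versus 167 subjects.

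- Pooled rate = (167 × 0.4395 + 334 × 0.5950)/501 = 0.5432.
- Null SE = √[0.5432 × 0.4568 × (1/167 + 1/334)] = 0.0472.
- Alternative SE = √[0.4395 × 0.5605/167 + 0.5950 × 0.4050/334] = 0.0469.
- Power = Φ[(0.1555 − 1.960 × 0.0472)/0.0469] = Φ(1.34) = 91.0%.

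This confirms at least 90% without any covariate. For the secondary SRI (44.8% versus 58.2%) the same formula gives 81.1%, against approximately 80% stated.

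**Adding the continuous score: smooth association.** The Protocol gives neither a Day 0 score distribution nor a score-response association within the two levels, so both are assumed: integer scores with mean 10.5 and SD 3.3, 58% at 10 or more. The model is logit P(response) = a + tT + g(S − mean), where T is treatment, S the score and g = ln(OR per SD)/SD. The terms a and t are set so that the marginal rates stay at 43.95% and 59.50%. Each scenario has 4000 trials of 501 subjects, 2:1 within the 9/10 levels, Wald test, with complement and region omitted. Under this distribution the split already carries 58% of the score variance.

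| OR per SD | Power, split | Power, split + score | Gain (points) | Log-OR (SE), split | Log-OR (SE), split + score |
|---|---|---|---|---|---|
| 1.0 | 90.6% | 90.6% | 0.0 | 0.631 (0.1924) | 0.633 (0.1928) |
| 1.2 | 90.7% | 90.9% | 0.2 | 0.636 (0.1929) | 0.639 (0.1937) |
| 1.5 | 91.8% | 92.2% | 0.4 | 0.645 (0.1948) | 0.657 (0.1968) |
| 2.0 | 92.8% | 93.4% | 0.6 | 0.678 (0.1990) | 0.705 (0.2037) |
| 2.5 | 93.2% | 94.5% | 1.3 | 0.696 (0.2032) | 0.741 (0.2104) |

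The SE rises in every row. Power improves because the estimate rises slightly more: at OR 2.5 the ratio goes from 0.696/0.2032 = 3.43 to 0.741/0.2104 = 3.52.

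**Adding the continuous score: with the floor.** A second simulation (3000 trials per scenario) assumed Day 0 scores from 2 to 24, 5% or 15% of subjects below 8, and no response below 4. Power with the split, then with the score added:

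| Log-odds slope per point | 5% below 8 | 15% below 8 |
|---|---|---|
| 0 | 90.8 → 90.7 | 90.9 → 91.6 |
| 0.05 | 91.3 → 91.4 | 91.0 → 91.4 |
| 0.10 | 91.1 → 91.3 | 92.0 → 93.2 |
| 0.20 | 92.6 → 93.4 | 92.3 → 94.2 |
| 0.30 | 93.2 → 94.4 | 93.5 → 95.7 |

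The change runs from −0.1 to +2.2 points. Simulation error on one power figure is about √(0.92 × 0.08/3000) = 0.5 points, and less on a paired difference. Under the null both models rejected in 4.4% to 6.1% of trials and differed by at most 0.25 points. A further run found gains of 0.5 to 1.7 points at slopes 0.10 to 0.30, and nothing beyond noise at slopes 0 and −0.10.

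**Room for the term.** The planning rates imply 73.4 + 198.7 = 272 responders and 501 − 272 = 229 non-responders. With treatment, three factors and the score, that is 229/5, about 46 per term.

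**The case against.** The strongest reply is that nothing here is an error. Adjusting at the stratification cut is a proper pre-specified choice, the sample size claims no benefit from covariates, and its power reproduces without any. That stands, and it makes this an optional improvement.

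A reader might go further and call the change free precision, or say that the plan discards the baseline score. Neither is supported. The standard error of the log odds ratio rises, the conditional odds ratio changes because odds ratios are non-collapsible, and the split keeps the main contrast. Nor can one claim that the term removes chance imbalance, since randomisation is already stratified on the screening score.

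It is also fair that prognostic strength is inferred. PGA, BILAG and the non-response rules also decide the outcome, and subjects with higher scores may fail those more often, so even the sign of the slope is assumed. Section 1.3.1 reports a larger belimumab benefit at higher activity; that is effect modification, which a main-effect term does not address. Nothing in the Protocol suggests that Day 0 scores below 4 are common, or shows how often the two proteinuria scorings differ at baseline. A covariate need not match the endpoint's baseline to be valid.

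These points limit the size of the claim. None shows harm from adding the term beside the existing factors. The two versions of the score are correlated with each other, but randomisation keeps them nearly unrelated to treatment.

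**Conclusion.** The point holds as a small refinement. Section 8.5.2 fixes a covariate list that leaves within-level baseline information unused and, as written, takes the score from a different proteinuria scoring than the endpoint. Adding the continuous score is worth about 0 to 2 percentage points of power in a trial already planned at about 91%, with no visible type I error cost. The upper end needs a fairly steep association within levels and a sizeable share of subjects below 8 at Day 0. Both are assumptions without a figure in the Protocol, and with a weak association the gain is indistinguishable from zero. It should not be inferred that the planned analysis is invalid, that the trial is underpowered or that a stated number is wrong.

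**What to change.** In section 8.5.2 and the Synopsis, keep treatment and the three factors as listed and add one term: the Day 0 total score with modified SLEDAI-2K proteinuria scoring, continuous and linear. In section 8.5.5, use the SELENA-scored Day 0 total for major secondary endpoint 1. State that the rule for dropping sparse factor levels does not apply to this term. Fix all of this before unblinding.

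The cost is one model term and no new data: the activity scales are scored at Day 0 (Table 6-1), and the Amendment 02 summary says the proteinuria modification is made programmatically. The price in interpretation is an odds ratio conditional on one more covariate. In the first simulation at OR 2.0 per SD it moves from exp(0.678) = 1.97 to exp(0.705) = 2.02, so the report should say what it conditions on. Linearity is an assumption and should be stated as such.

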### **8.5.2.1. Subgroup Analysis**

Subgroup analysis, of SRI only, will be performed in the following subgroups:

- Baseline SELENA SLEDAI score ( $\leq 9$  vs  $\geq 10$ ).
- Baseline anti-dsDNA ( $\geq 30$  IU/mL vs  $< 30$  IU/mL).
- Baseline prednisone dose level ( $\leq 7.5$  mg/day vs  $> 7.5$  mg/day).
- Baseline complement levels (C3 and/or C4 low vs other).
- Baseline complement and anti-dsDNA (C3 and/or C4 low AND anti-dsDNA  $\geq 30$  IU/mL vs other)\*.
- Region (US/Canada vs other).

A multivariate analysis will also be performed to evaluate how response to belimumab relative to placebo varied across different categories within relevant baseline demographic or disease characteristics. The details will be described in the analysis plan.

\*Additional efficacy endpoint analyses in this subgroup will be performed and will be described in the analytical plan.

### **8.5.3. Secondary Efficacy Endpoints**

The major secondary efficacy endpoints include:

1. SRI response rate with the SELENA SLEDAI for scoring of proteinuria at Week 52.
2. Time to first severe flare (as measured by the modified SLE Flare Index; with SLEDAI-2K and SELENA SLEDAI as the SLEDAI criterion of the SFI).
3. Percent of subjects whose average prednisone dose has been reduced by  $\geq 25\%$  from baseline to  $\leq 7.5$  mg/day during Weeks 40 through 52, in subjects receiving greater than 7.5 mg/day at baseline.

### **8.5.4. Other Efficacy Endpoints**

**Endpoints Supporting Primary Efficacy Endpoint (SRI where SELENA SLEDAI score is modified to use the SLEDAI-2K scoring for proteinuria):**

1. SRI by visit.
2. Percent of subjects with a  $\geq 4$  point reduction from baseline in SELENA SLEDAI (modified to use the SLEDAI-2K scoring for proteinuria) at Week 52 and by visit.
3. Percent of subjects with no new BILAG A organ domain score or 2 new BILAG B organ domain scores compared with baseline at Week 52 and by visit.
4. Percent of subjects without PGA worsening (increase of  $< 0.30$  points from baseline) at Week 52 and by visit.
5. Percent of subjects with durable SRI from Week 44-52.
6. Time to the 1st SRI that is maintained through Week 52.
7. Duration of longest response among subjects with at least 1 SRI response.
8. SRI 5-8 at Week 52 and by visit.

The SRI 5-8 are defined identically to the SRI except for using higher thresholds of improvement for SELENA SLEDAI (modified to use the SLEDAI-2K scoring for proteinuria) reduction for a patient to be declared a responder (eg, SELENA SLEDAI  $\geq 5$  point reduction for SRI5).

**Disease activity:**

1. Mean percent change and mean change in PGA by visit.
2. Mean percent change and mean change in SELENA SLEDAI with the modified SLEDAI-2K scoring for proteinuria score by visit.

**Organ Specific:**

1. Percent of subjects with organ improvement by SELENA SLEDAI by visit. The renal domain will use the SLEDAI-2K proteinuria scoring as the primary method with the SELENA SLEDAI proteinuria scoring as a sensitivity analysis.
2. Percent of subjects with organ worsening by SELENA SLEDAI by visit. The renal domain will use the SLEDAI-2K proteinuria scoring as the primary method with the SELENA SLEDAI proteinuria scoring as a sensitivity analysis.
3. Percent of subjects with organ improvement by BILAG by visit.
4. Percent of subjects with organ worsening by BILAG by visit.
5. Mean/median percent (in patients with proteinuria at baseline) and mean/median absolute (in all patients) change in proteinuria by visit.
6. Time to renal flare over 52 weeks (see definition below).
7. Percent of patients developing at least 1 renal flare (see definition below) over 52 weeks.
8. Percent of subjects with doubling of serum creatinine (the proportion of patients whose serum creatinine attains a level double that of the baseline value and is confirmed with a second measurement at least 3 weeks later).

**SFI Flare (SFI where SELENA SLEDAI score is modified to use the SLEDAI-2K scoring for proteinuria):**

1. Time to flare over 52 weeks.
2. Time to flare after Week 24.
3. Time to severe flare after Week 24.
4. Rate of flare per 100 subject years.
5. Rate of severe flare per 100 subject years.

